#### **7.4.4. Visit 05, Day 92, Second Vaccination (Dose 2), Clinic Visit (Window: 91±14 days post first study vaccination)**

- Interim medical history, including an assessment for new medical conditions will be obtained by interview of parent(s)/legal guardian(s) and any changes since the previous clinic visit or contact will be noted.
- Criteria for administering QIV will be reviewed with parent(s)/legal guardian(s).
- Concomitant medications (limited to aspirin or salicylate containing products) will be recorded on the appropriate data collection form.
- All AESIs/NOCMCs/SAEs will be recorded on the appropriate data collection form. Reporting of AEs occurring since previous visit but before 2nd vaccination is limited to AESIs, NOCMCs, and SAEs.
- A targeted physical examination may be performed prior to the second study vaccination, if indicated based on review of interim medical history, by a study clinician licensed to make medical diagnoses and listed on the Form FDA 1572 as the site principal investigator or sub-investigator.
- Subject's/parent(s)/legal guardian(s) will be counseled on the avoidance of taking any aspirin or salicylate containing products for 30 days prior to receipt of the first vaccination through 21 days after the last vaccination.
- Oral temperature will be obtained to ensure eligibility. Subjects must not eat or drink anything hot or cold, or smoke within 10 minutes prior to taking oral temperature.
- A urine pregnancy test will be performed on all female adolescent subjects of childbearing potential and must be negative to ensure eligibility.
- A nasal swab for sIgA will be obtained.
- Approximately 6 mL of venous blood will be collected for serum HAI, HA/NA ELISA and neutralization assays.
- Approximately 16 mL of PBMCs will be collected for IFN- $\gamma$  ELISPOT and CFSE dilution/ICS assays. Note: PBMCs will not be collected if the HgB was consistently low through Day 57.
- Subjects will receive their second vaccination IM in whichever deltoid they prefer.

- Subjects will receive a single dose of study vaccine via IM injection into the deltoid muscle of the preferred arm. The site of injection and time of administration will be recorded on the appropriated data collection form. Subjects will be observed in the clinic for at least 30 minutes after the second study vaccination.

#### **7.4.5. Visit 06, Day 113, Clinic Visit**

**(Window: 21±2 days post second study vaccination)**

- Interim medical history, including an assessment for new medical conditions will be obtained by interview of parent(s)/legal guardian(s) and any changes since the previous clinic visit or contact will be noted.
- Concomitant medications (limited to aspirin or salicylate containing products) will be recorded on the appropriate data collection form.
- All SAEs will be recorded on the appropriate data collection form.
- A targeted physical examination may be performed, if indicated based on review of interim medical history, by a study clinician licensed to make medical diagnoses and listed on the Form FDA 1572 as the site principal investigator or sub-investigator.
- Subject's/parent(s)/legal guardian(s) will be counseled on the avoidance of taking any aspirin or salicylate containing products for 30 days prior to receipt of the first vaccination through 21 days after the last vaccination.
- In the event that the subject attends the visit without a parent/legal guardian, the parent/legal guardian will be called to collect updated medical history, concomitant medications, and will be reminded that the subject is to avoid any aspirin or salicylate containing products for 30 days prior to receipt of the first vaccination through 21 days after the last vaccination.
- A nasal swab for sIgA will be obtained.
- Approximately 6 mL of venous blood will be collected for serum HAI, HA/NA ELISA and neutralization assays.
- Approximately 16 mL of PBMCs will be collected for IFN- $\gamma$  ELISPOT and CFSE dilution/ICS assays. Note: PBMCs will not be collected if the HgB was consistently low through Day 57.

- Approximately 8 mL of venous blood will be collected for Hgb and Ferritin level. If the ferritin level is < 15 ng/mL and/or the Hgb is less than the lower limits of normal, recommend follow-up with primary care provider for consideration of multivitamins with iron.

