#### **3.2. Study Outcome Measures**

##### **3.2.1. Primary:**

Safety:

- Frequency of solicited upper respiratory and systemic reactogenicity through approximately Day 8 after the first study vaccination.

- 
- Frequency of unsolicited non-serious adverse events from the time of study vaccination through 21 days after the first study vaccination.
  - Frequency of SAEs, regardless of seriousness or relationship to study vaccination, from receipt of the first vaccination throughout the entire study.
  - Frequency of New Onset Chronic Medical Conditions (NOCMC) and AESIs that develop from receipt of vaccination through 3 months after first study vaccination.

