## 4. STUDY DESIGN

This is a Phase I double-blind, randomized, placebo-controlled study in 50 healthy adolescents and children, 9-17 years of age, who are in good health and meet all eligibility criteria. The study is designed to assess the safety and immunogenicity of a prime-boost regimen of H3N2 M2SR intranasal influenza vaccine followed by licensed inactivated QIV boost administered IM. Group A will receive one dose of M2SR intranasally on Day 1 and one dose of QIV on Day 92. Group B will receive one dose of saline intranasally on Day 1, and one dose of QIV on Day 92. See Table 1 for the randomization scheme for this trial.

The two treatment arms will be enrolled and vaccinated concurrently.

Reactogenicity will be measured by the occurrence of solicited upper respiratory, respiratory tract assessment, and systemic reactions from the time of the experimental (first) study vaccination through 7 days after vaccination. Unsolicited non-serious AEs will be collected from the time of the first study vaccination through approximately 21 days after the first study vaccination. SAEs will be collected from the time of the first study vaccination throughout the entire study. AESIs (wheezing, and otitis media) and NOCMC will be documented and reported from the time of first study vaccination through approximately 3 months after first study vaccination.

Immunogenicity testing will include performing HAI, HA/NA ELISA, neutralization, nasal secretory IgA (sIgA), IFN- $\gamma$  ELISPOT and CFSE dilution/ICS assays. Serum for HAI, HA/NA ELISA and neutralization assays will be obtained on Day 01 (pre-vaccination), Days 08, 22, and 57 after the first vaccination, immediately prior to the 2nd study vaccination (Day 92), and on Day 22 after the 2nd vaccination. Nasal swabs for sIgA will be collected on Day 01 (pre-vaccination), Days 08, 22, and 57 after the first vaccination, immediately prior to the 2nd vaccination (Day 92), and on Day 22 after the 2nd vaccination. PBMC for T cell functional assays (IFN- $\gamma$  ELISPOT and CFSE dilution/ICS assays) will be harvested on Day 01 (pre-vaccination), Days 08, 22, and 57 after the first vaccination, immediately prior to 2nd vaccination (Day 92), and on Day 22 after the 2nd vaccination.

The duration of this study for each subject will be approximately 13 months.

---

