#### **7.4.1. Visit 02, Day 08, Clinic Visit**

##### **(Window: 7±1 days post first study vaccination)**

- Interim medical history, including an assessment for new medical conditions will be obtained by interview of parent(s)/legal guardian(s) and any changes since the previous clinic visit or contact will be noted.
- Subject's parent(s)/legal guardian(s) will be asked if the subject had any additional blood taken for medical reasons.
- Memory aid information will be reviewed with parent(s)/legal guardian(s).
- All concomitant medications (including solicitation for receipt of any non-study influenza vaccines) will be recorded on the appropriate data collection form prior to the second study vaccination.
- Subject's/parent(s)/legal guardian(s) will be counseled on the avoidance of taking any aspirin or salicylate containing products for 30 days prior to receipt of the first vaccination through 21 days after the last vaccination.
- All AE/AESIs/NOCMCs/SAEs will be recorded on the appropriate data collection form.
- In the event that the subject attends the visit without a parent/legal guardian, the parent/legal guardian will be called to collect updated medical history, concomitant medications, and will be reminded that the subject is to avoid any aspirin or salicylate containing products for 30 days prior to receipt of the first vaccination through 21 days after the last vaccination.
- A limited physical examination to specifically include the nares (including edema), throat, and lungs (including evaluation for wheezing) will be performed and a targeted physical examination may be performed on the other body systems if indicated based on review of interim medical history, by a study clinician licensed to make medical diagnoses and listed on the Form FDA 1572 as the site principal investigator or sub-investigator.
- A nasal swab for sIgA will be obtained.
- Approximately 14 mL of venous blood will be collected for safety labs including WBC, HGB, Platelet Count, ALT, AST, Serum Creatinine, PT and aPTT.
- Approximately 6 mL of venous blood will be collected for serum HAI, HA/NA ELISA and neutralization assays.

- Approximately 16 mL of PBMCs will be collected for IFN- $\gamma$  ELISPOT and CFSE dilution/ICS assays.

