**New-Onset Chronic Medical Conditions (NOCMCs):** NOCMCs are defined as any new ICD-10 diagnosis that is applied to the subject during the duration of the study, after receipt of the study agent, that is expected to continue for at least 3 months and requires continued health care intervention.

**Severity of Event:** AEs will be assessed by a licensed study physician listed on the Form FDA 1572 as the site principal investigator or appropriate sub-investigator using a protocol-defined grading system (see [Sections 9.2.2](#) and [9.2.3](#)). For events not included in the protocol-defined grading system, the following guidelines will be used to quantify severity:

- **Mild (Grade 1):** Events require minimal or no treatment and do not interfere with the subject's daily activities.

- **Moderate (Grade 2):** Events result in a low level of inconvenience or concern with therapeutic measures. Moderate events may cause some interference with functioning and daily activities.
- **Severe (Grade 3):** Events interrupt the subject’s daily activities and may require systemic drug therapy or other treatment. Severe events are usually incapacitating.

**Relationship to Study Product:** The licensed study physician’s assessment of an AE's relationship to study product is part of the documentation process, but it is not a factor in determining what is or is not reported in this trial. If there is any doubt as to whether a clinical observation is an AE, the event should be reported. The relationship to study product must be assessed for AEs using the terms: related or not related. In a clinical trial, the study product must always be suspect. To help assess, the following guidelines are used:

- **Related** – There is a reasonable possibility that the study product caused the AE. Reasonable possibility means that there is evidence to suggest a causal relationship between the study product and the AE.
- **Not Related** – There is not a reasonable possibility that the administration of the study product caused the event.

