#### 9.2.4. Adverse Events of Special Interest (AESI)

- Medically significant wheezing: defined as wheezing on physical exam sign of respiratory distress (tachypnea, retractions, or dyspnea), hypoxemia (O2 saturation < 95%), or new bronchodilator prescription, or use of daily bronchodilator therapy (not on an “as needed” basis) from receipt of the first vaccination through 3 months after the first vaccination. Will record presence or absence of any wheezing after V02 and whether wheezing is diffuse or localized, respiratory rate, oxygen saturation, medications associated with wheezing, and physician’s description on auscultation.
- Otitis Media and Wheezing at V02 only will be graded as follows:

Systemic (Quantitative)	Mild (Grade 1)	Moderate (Grade 2)	Severe (Grade 3)
Otitis Media	No interference with daily activity	Some interference with daily activity	Significant interference, prevents daily activity
Wheezing	No interference with daily activity	Some interference with daily activity	Significant interference, prevents daily activity

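### AESIs and NOCMCs are a primary outcome through 3 months after dose 1, but their last scheduled assessment, Visit 05, may fall at day 77, and Visit 06 lists only SAEs for recording

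*Protocol*

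**What the plan says.** **Endpoint.** Protocol 3.2.1, repeated in SAP 3.2.1, lists as a primary outcome "Frequency of New Onset Chronic Medical Conditions (NOCMC) and AESIs that develop from receipt of vaccination through 3 months after first study vaccination". Protocol section 4 is looser: "AESIs (wheezing, and otitis media) and NOCMC will be documented and reported from the time of first study vaccination through approximately 3 months" after that vaccination. Protocol 9.3 and 9.4 also say approximately 3 months.

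**Schedule.** The AESI + NOCMC row in Appendix A and in SAP Table 2 is marked at V02, V03, V04 and V05 and is blank at V06 to V08. It is also marked for early termination and unscheduled visits that fall within 3 months of dose 1.

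**Visit 05.** Protocol 7.4.4 gives "Window: 91±14 days post first study vaccination", and SAP 4.4.5 states the same window as 77 to 105 days. AESIs, NOCMCs and SAEs are recorded there.

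**Visit 06.** Protocol 7.4.5 asks for an interim history that includes new medical conditions. Its event line reads "All SAEs will be recorded on the appropriate data collection form" and names neither AESIs nor NOCMCs.

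**NOCMC definition.** Protocol 9.2.1 counts "any new ICD-10 diagnosis that is applied to the subject during the duration of the study" after the study agent, if it is expected to last at least 3 months and needs continued care.

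**Otitis media.** It is one of the two AESIs. Protocol 2.3.1 includes ear infections among the effects of live intranasal vaccines that the trial says it will study as solicited events. For Visit 02, Protocol 7.4.1 says "A limited physical examination to specifically include the nares (including edema), throat, and lungs (including evaluation for wheezing) will be performed", and Protocol 9.2.4 says "Otitis Media and Wheezing at V02 only will be graded as follows".

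**The concern.** The outcome is defined by elapsed time, but its planned ascertainment ends at a visit that may come two weeks before that time is up. Children are then counted as followed for 3 months although the last planned question about these events came at different times. A condition that begins after an early Visit 05, and is mentioned in the Visit 06 history, has no instruction sending it to the AESI or NOCMC form.

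Few such events are expected, so each one counts. Protocol 11.4.2 tabulates these events by arm and applies Fisher's exact test only if more than 5% of subjects report them. Of 50 subjects, 2 is 4% and 3 is 6%, so one unrecorded event can decide whether a comparison is made at all.

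The NOCMC and otitis texts raise a related problem. The definition, the solicited list and the examination list do not describe the same ascertainment, so a reader of the study report would not know how thoroughly these events were sought.

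**Working it through.** **Inputs.** Visit 05 window 91 ± 14 days (Protocol 7.4.4). Visit 06 window 21 ± 2 days after dose 2 (Protocol 7.4.5). The documents do not give 3 months in days. I take 91, the nominal Visit 05 day, and show 90 to 92.

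**1. The plan's own figure.** 91 − 14 = 77 and 91 + 14 = 105, which matches SAP 4.4.5. Protocol 6.3 writes the window as Day 92 ± 14 days after the first vaccination. Read literally, that is 78 to 106 days, which shortens the largest gap below by one day.

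**2. Largest gap after the last scheduled assessment.** Gap = (length of 3 months) − (day of Visit 05), or zero if negative. With Visit 05 at day 77:

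| 3 months taken as | Gap | Share of period |
|---|---|---|
| 90 days | 13 days | 14.4% |
| 91 days | 14 days | 15.4% |
| 92 days | 15 days | 16.3% |

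The gap is zero when Visit 05 is at day 91 or later.

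**3. How much of the window is exposed.** Days 77 to 105 are 29 permitted days, of which 14 (77 to 90) precede day 91.

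**4. Average gap if Visit 05 dates are uniform (assumption).** Counting whole days, (14 + 13 + … + 1)/29 = 105/29 = 3.6 days. Treated as continuous, half the children have a mean gap of 7 days and half have none, so 0.5 × 7 = 3.5 days. Either way this is about 4% of 91 days.

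**5. Whether Visit 06 closes the gap.** With Visit 05 at day 77, Visit 06 falls between 77 + 19 = 96 and 77 + 23 = 100 days after dose 1. That is beyond 3 months on any of the three definitions. Any later Visit 05 moves Visit 06 later still.

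**6. NOCMC texts side by side.** The definition in Protocol 9.2.1 runs for the whole study. Protocol 3.2.1, 9.1, 9.3 and 9.4 stop at 3 months or approximately 3 months. A condition first diagnosed at month 6 meets the definition but falls outside the outcome.

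**7. Otitis texts side by side.** Protocol 2.3.1 promises that ear infections will be solicited. No ear symptom is in the solicited lists of Protocol 8.1 or SAP 9.3.1, or in the grading tables of Protocol 9.2.2. SAP Tables 40 to 43 have a wheezing row but none for otitis media. The mandatory Visit 02 examination names nares, throat and lungs, while Protocol 9.2.4 grades otitis media at that same visit.

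**The case against.** The best reply is that the documents treat Visit 05 as the 3-month point. SAP 4.4.5 describes the second vaccination as given about 3 months after the first and then states the 77-to-105-day window, and several sections say approximately 3 months. On that view the gap is ordinary visit tolerance, zero at the nominal day and small on average. This limits the size of the problem. It does not remove it, because the outcome in 3.2.1 carries no such tolerance and nothing is asked about the remaining days.

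It can also be said that stopping at dose 2 suits an objective about M2SR, since later events are confounded with QIV. That is a fair reason to identify such events. It is not a reason to leave them out of an outcome defined by time from dose 1.

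Other routes exist. Unscheduled and early termination visits collect these events until 3 months, and Protocol 9.2.7 and 9.4 impose general duties to record and follow them. None of these schedules a question about the days after an early Visit 05 or says where the Visit 06 history should go. Protocol 8.1 lets new medication prompt an AESI or NOCMC evaluation, but from Visit 04 Appendix A limits medication collection to aspirin and salicylate products.

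Two stronger readings are tempting and are not supported:

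- **A missed Visit 05.** A reader might infer that such a child is last assessed at Visit 04 and loses 91 − 56 = 35 days (38%). Protocol 5.3.4 encourages one-dose subjects to continue safety follow-up, by telephone if needed, to about 3 months. It also requires repeated contact attempts after a missed safety assessment. Visit 06 is timed from dose 2, so recording there would not help a child who never received it.
- **Ears never examined after dosing.** Protocol 7.4.1 to 7.4.5 and 8.1 allow a targeted examination when the history indicates one. What is absent is a mandatory or named ear examination.

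**Conclusion.** The point stands as a modest and easily corrected gap in ascertaining a primary safety outcome. It affects only children whose Visit 05 comes before about day 91. For them, up to 14 of 91 days (13 to 15 days if 3 months is 90 to 92 days) have no scheduled ascertainment. The average of about 3.5 days rests on uniform Visit 05 dates, which the documents do not give.

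No event rates are given for AESIs or NOCMCs, so the number of events missed cannot be estimated. A reader might infer bias between the arms. The documents do not support that, because assessors are blinded and both arms follow the same schedule. The likely harm is under-recording in both.

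The NOCMC definition and the otitis provisions are separate inconsistencies of wording that need reconciling. As written, otitis media is found through history and a discretionary examination, and its count should be read in that light.

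**What to change.** 1. In Protocol 7.4.5, add that AESIs and NOCMCs with onset within 3 months of dose 1 are recorded at Visit 06, and mark the AESI + NOCMC row for V06 in Appendix A and SAP Table 2. State 3 months in days.
2. Use the column already in SAP Tables 50 and 51 that shows which vaccination had been received when the event occurred, so that onsets after an early QIV can be told apart.
3. Reconcile the NOCMC definition in Protocol 9.2.1 with the collection period in 3.2.1, 9.3 and 9.4.
4. Reconcile Protocol 2.3.1 with the solicited lists (Protocol 8.1, SAP 9.3.1), the Visit 02 examination (7.4.1) and the grading in 9.2.4. Alternatively, state that otitis ascertainment rests on history and a discretionary targeted examination.

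The cost is wording and a few more events to record. No visit or sample is added, since the history is already taken at Visit 06. Protocol 14.8 refers to a time after all subjects had enrolled. If the Visit 06 contacts are already past, review the histories taken there and at the Day 240 call for onsets within 3 months. Report the actual day of each child's last AESI/NOCMC assessment, and give the remaining gap as a limitation.

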#### **7.4.6. Visit 07; Day 240, Phone Call**

**(Window: 148±14 days post second vaccination)**

- Study personnel will contact parent(s)/legal guardian(s) by phone to solicit any SAEs, medical history information that have occurred since the previous clinic visit will be solicited. Based on the information, subjects may be asked to return to the clinic for evaluation.

#### **7.5. Final Study Visit, Visit 08, Day 366, Phone Call**

**(Window: 274±14 days post second vaccination)**

- Study personnel will contact parent(s)/legal guardian(s) by phone to solicit any SAEs, medical history information that have occurred since the previous clinic visit will be solicited. Based on the information, subjects may be asked to return to the clinic for evaluation.

#### **7.6. Early Termination Visit (if needed)**

The following activities will be performed at the early termination visit on subjects who withdraw, or are withdrawn or terminated from this trial:

- Interim medical history, including an assessment for new medical conditions will be obtained by interview of parent(s)/legal guardian(s) and any changes since the previous clinic visit or contact will be noted.
- Memory aid information will be reviewed with parent(s)/legal guardian(s) (if within 8 days after the last study vaccination).
- All concomitant medications (including solicitation for receipt of any non-study influenza vaccines) will be recorded on the appropriate data collection form (if within 21 days after the first study vaccination). If within 30 days of either vaccination through 21 days after the last vaccination, aspirin or salicylate containing products will be recorded.

- 
- Subject's/parent(s)/legal guardian(s) will be counseled on the avoidance of taking any aspirin or salicylate containing products for 30 days prior to receipt of the first vaccination through 21 days after the last vaccination.
  - All AE/AESIs/NOCMCs/SAEs will be recorded on the appropriate data collection form. AEs will be limited to AESIs and SAEs if after 21 days the first study vaccination. AESIs and NOCMCs will be collected until 3 months and SAEs will be collected throughout the entire study.
  - In the event that the subject attends the visit without a parent/legal guardian, the parent/legal guardian will be called to collect updated medical history, concomitant medications, and will be reminded that the subject is to avoid any aspirin or salicylate containing products for 30 days prior to receipt of the first vaccination through 21 days after the last vaccination.
  - Oral temperature may be obtained if indicated. Subjects must not eat or drink anything hot or cold, or smoke within 10 minutes prior to taking oral temperature.
  - A limited physical examination to specifically include the nares (including edema), throat, and lungs will be done if within 8 days after first vaccination.
  - A targeted physical examination may be performed prior to the second study vaccination, if indicated based on review of interim medical history, by a study clinician licensed to make medical diagnoses and listed on the Form FDA 1572 as the site principal investigator or sub-investigator.
  - A nasal swab for sIgA will be obtained.
  - Approximately 6 mL of venous blood will be collected for serum HAI, HA/NA ELISA and neutralization assays.
  - Approximately 16 mL of PBMCs will be collected for IFN- $\gamma$  ELISPOT and CFSE dilution/ICS assays. Note: PBMCs will not be collected if the HgB was consistently low through Day 57.

